12.2 Treatment Exposure

Extent of treatment exposure for completed or discontinued subjects will be calculated in days using the following:

Extent of Exposure (days) = (Date of Study Completion/Discontinuation – Date of Day 1) + 1

Extent of treatment exposure (days) for each subject exposed to study drug will be summarized with continuous descriptive statistics for each treatment group, using the Safety population. A subject listing of treatment exposure and dosing compliance will also be produced.

13. Efficacy Analyses

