- Note: If only one eye qualifies then the single qualifying eye will be the study eye. In the case that both eyes are eligible for analysis, the study eye will be the eye with worse (higher) central corneal fluorescein staining at Visit 2. If the central corneal fluorescein staining is the equivalent in both eyes, then the right eye will be selected as the study eye.
- **Randomization** – subjects will be randomized according to the following two strata:
 1. Visit 2 study eye CCSS █ and
 2. Visit 1 CCSS minus Visit 2 CCSS (V1 CCSS - V2 CCSS); difference in study eye CCSS █
- **Blood Sampling** Blood samples will be collected from all subjects for immunogenicity testing █

- Study Drug Instillation at the Study Site All subjects meeting all other screening eligibility criteria after Visit 2 will be randomized to one of two treatment arms. Randomized subjects will self-administer their initial study drug dose bilaterally at the study site.
- Ora Calibra® Drop Comfort Assessments The Ora Calibra® Drop Comfort Scale will be performed immediately after instillation and then at 1, 2, and 3 minutes following instillation.
- Monitoring and Query of AEs
- Study Drug Dispensation Prior to discharge from the study site on Visit 2 (Day 1), randomized subjects will be educated in the self-administration of study drug. The initial, self-administered dose taken in-office at Visit 2 will be counted as a morning dose regardless of visit time, and subjects will be instructed to administer an evening dose that night. Subjects will receive their assigned study drug kit with sufficient supply to last until Visit 3 and will be instructed NOT to self-administer study drug on the morning of their next scheduled study visit (Visit 3, Day 8).
- Schedule Next Visit Subjects will be scheduled for Visit 3.

8.4.4 Visit 3: Day 8 ± 1 –Week 1

- Study Drug Collection All used/unused study drug vials dispensed for Days 1 to 8 should be collected and reviewed by a trained study technician.
- Site staff must confirm that subjects have NOT administered their morning study drug dose at home. If subject dosed prior to the visit, study visit procedures should begin 4 hours after time of dosing.
- Monitoring and Query AEs
- Recording of all Changes in Concomitant Medications
- Ora Calibra® Ocular Discomfort Scale
- Ora Calibra® Ocular Discomfort & 4-Symptom Questionnaire
- VAS
- OSDI[©]
- BCVA Utilizing an ETDRS Chart
- Slit-Lamp Biomicroscopy
- Conjunctival Redness
- TFBUT

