8.4.6 Visit 5: Day 29 ± 2 –Week 4

- Study Drug Collection All used/unused study drug vials dispensed for Days 15 to 29 should be collected and reviewed by a trained study technician.
- Site staff must confirm subjects have NOT administered their morning study drug dose at home. If subject dosed prior to the visit, study visit procedures should begin 4 hours after time of dosing.
- Monitoring and Query of AEs
- Record all Changes in Concomitant Medications
- Ora Calibra® Ocular Discomfort Scale
- Ora Calibra® Ocular Discomfort & 4-Symptom Questionnaire
- VAS
- OSDI[®]
- BCVA Utilizing an ETDRS Chart
- Slit-Lamp Biomicroscopy
- Conjunctival Redness
- TFBUT
- Corneal and Conjunctival Staining (fluorescein)
- Corneal and Conjunctival Staining (lissamine green)
- Schirmer's Test
- [REDACTED]
- Monitoring and Query of AEs

- Study Drug Dispensation Prior to discharge from the study site on Visit 5 (Day 29), subjects will be educated in on self-administration of study drug. Subjects will receive two new assigned study drug kits with sufficient supply to last until Visit 6 and will be instructed to NOT self-administer study drug on the morning of their next scheduled study visit (Visit 6, Day 57 ± 3). Subjects will self-administer morning dose after visit is complete, regardless of the time, and instructed to administer an evening dose that night.

- Schedule Next Visit Subjects will be scheduled for Visit 6.

8.4.7 **Visit 6: Day 57 ± 3 –Week 8 and Study Exit**

- Study Drug Collection All used/unused study drug vials dispensed for Days 29 to 57 should be collected and reviewed by a trained study technician.
- Site staff must confirm subjects have NOT administered their morning study drug dose at home. If subject dosed prior to the visit, study visit procedures should begin 4 hours after the time of dosing.
- Monitoring and Query of AEs
- Record all Changes in Concomitant Medications
- Urine Pregnancy Test (for females of childbearing potential)
- Ora Calibra® Ocular Discomfort Scale
- Ora Calibra® Ocular Discomfort & 4-Symptom Questionnaire
- VAS
- OSDI[©]
- BCVA Utilizing an ETDRS Chart
- Slit-Lamp Biomicroscopy
- Conjunctival Redness
- TFBUT
- Corneal and Conjunctival Staining (fluorescein)
- Corneal and Conjunctival Staining (lissamine green)
- Schirmer's Test
- Intraocular Pressure
- Dilated Fundoscopy
- Blood Sampling for Immunogenicity Testing [REDACTED]
- Study Exit

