12.1 Dosing Compliance

Dosing compliance will be calculated as:

$$\text{Dosing Compliance (\%)} = (\text{Number of doses taken from Day 1 to study completion/discontinuation visit} / \text{Number of expected doses from Day 1 to study completion/discontinuation visit}) * 100$$

The number of doses taken will be calculated by subtracting the number of unused vials from the number of vials dispensed plus the total number of vials missed reported in the electronic case report form (eCRF). For subjects who do not receive a dose of randomized study drug, the number of expected doses will be 0 and compliance will be defined as 0. Otherwise, the number of expected doses will be calculated as $2 \times [\text{Date of Study Completion/Discontinuation} - \text{Date of Day 1} + 1]$. If a subject discontinues on Day 1 then the number of expected doses is 1.

Dosing compliance will be summarized using continuous descriptive statistics including mean, SD, median, minimum, and maximum for the Safety Population. Additionally, a categorical summary display frequencies and percentages of those deemed compliant, under-compliant (<80%), and over-compliant (>125%).

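### The SAP's compliance and exposure formulas count the exit day as a full dosing day, so a fully adherent Day 57 completer scores 98.2% with 57 exposure days instead of 56

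*SAP*

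**What the plan says.** SAP 12.2 states: "Extent of treatment exposure for completed or discontinued subjects will be calculated in days using the following", and then gives the formula "Extent of Exposure (days) = (Date of Study Completion/Discontinuation – Date of Day 1) + 1". SAP 12.1 uses the same day count for compliance: "Otherwise, the number of expected doses will be calculated as" two times the number of days from Day 1 to exit, both ends included. An exit on study Day D thus gives 2D expected doses and D exposure days. There is one exception for early exits: "If a subject discontinues on Day 1 then the number of expected doses is 1". Subjects who never dosed are assigned zero expected doses and zero compliance.

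On use, SAP 12.1 says: "Dosing compliance will be summarized using continuous descriptive statistics including mean, SD, median, minimum, and maximum for the Safety Population". It adds a table of compliant, "under-compliant (<80%), and over-compliant (>125" per cent) subjects.

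The protocol sets out which doses fall on which days:

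- **Day 1 (8.4.3):** "The initial, self-administered dose taken in-office at Visit 2 will be counted as a morning dose regardless of visit time", with an evening dose that night, so two doses.
- **Days 8, 15 and 29 (8.4.4 to 8.4.6):** the first dose is taken after the assessments and the second that evening, so two doses.
- **Visit 6 (8.4.6 and 8.4.7):** at Visit 5 subjects are "instructed to NOT self-administer study drug on the morning of their next scheduled study visit (Visit 6, Day 57" ± 3). At Visit 6 all used and unused vials are collected and the subject exits.
- **Early termination visit (8.4.11):** drug is collected. Nothing is said about the morning dose.

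Protocol 8.8 and SAP 3.1 both give 56 days of treatment.

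**The concern.** A subject who follows the instructions takes no dose on the day of Visit 6, yet the SAP expects two doses on that day and counts it as a day of exposure. Perfect adherence by a completer cannot reach 100%, and exposure runs one day beyond the last day of dosing. The loss is proportionally largest for short stays, where two extra expected doses can move a subject across the 80% limit. The Day 1 exception shows that the SAP already treats one exit day as less than a two-dose day, but the adjustment stops there and expected doses jump from 1 to 4 for a Day 2 exit.

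Both formulas also run to study exit, not to the last dose. The estimands in SAP 2.6 provide for subjects who stop study medication and are still measured. For them, exposure includes time off drug, and that error is not limited to one day.

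At stake are the reported compliance and exposure figures, and the labels of subjects close to 80%.

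**Working it through.** **Inputs.** Expected doses 2D for an exit on Day D > 1, and 1 for D = 1 (SAP 12.1). Exposure D days (SAP 12.2). Two doses on each day before exit (Protocol 8.4.3 to 8.4.6). No dose on the day of Visit 6 if instructions are followed (Protocol 8.4.6, 8.4.7). Under-compliance below 80% (SAP 12.1).

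**Step 1: the plan's own duration.** Dosing days for a Day 57 exit are 57 − 1 = 56, which reproduces the 56 days in Protocol 8.8 and SAP 3.1. The SAP 12.2 formula gives 57 − 1 + 1 = 57.

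**Step 2: score for perfect adherence.** With no exit-day dose the score is 2(D − 1)/2D. With one morning dose on the exit day it is (2D − 1)/2D.

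| Exit day | Expected (SAP) | No exit-day dose | One exit-day morning dose |
|---|---|---|---|
| 1 | 1 | 1/1 = 100% (exempt) | same |
| 2 | 4 | 2/4 = 50.0% | 3/4 = 75.0% |
| 3 | 6 | 4/6 = 66.7% | 5/6 = 83.3% |
| 4 | 8 | 6/8 = 75.0% | 7/8 = 87.5% |
| 5 | 10 | 8/10 = 80.0% | 9/10 = 90.0% |
| 57 | 114 | 112/114 = 98.2% | 113/114 = 99.1% |

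Across the Visit 6 window with no exit-day dose, the score is 106/108 = 98.1% at Day 54 and 118/120 = 98.3% at Day 60. A Day 5 exit sits exactly at 80% and is not below it.

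**Step 3: the 80% limit for a Day 57 completer.** On the SAP denominator, 0.80 × 114 = 91.2, so at least 92 doses are needed. On doses due, 0.80 × 112 = 89.6, so at least 90. Only 90 and 91 doses change category:

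- 90 doses: 90/114 = 78.9% (SAP) against 90/112 = 80.4%.
- 91 doses: 91/114 = 79.8% (SAP) against 91/112 = 81.3%.

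**Step 4: exposure after stopping drug.** As an illustration, a subject whose last dose is on Day 29 and who is measured and exits on Day 57 is given 57 exposure days; to the last dose it is 29 − 1 + 1 = 29. The documents do not say how many such subjects to expect.

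**Step 5: check of the replacement.** Dropping the exit day without qualification would set expected doses for a Day 2 exit at 2, so a subject with three doses (two on Day 1, one on the Day 2 morning) would score 3/2 = 150% and be labelled over-compliant. Adding one expected dose when an exit-day dose is recorded gives 3/3 = 100%. The Day 57 completer then scores 112/112, or 113/113 with an exit-day dose.

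**The case against.** The best defence is that this is a disclosed, reproducible convention applied equally to both arms, and that the protocol synopsis itself labels the treatment period 57 ± 3 days. For completers the difference is one day in 57, under 2%. Both outputs are descriptive, the estimands ignore non-optimal compliance, and no test uses either figure. All of this stands, and it limits the point's importance. It does not make the figures right: the denominator still includes two doses that subjects following the Visit 6 instruction do not take, and Protocol 8.8 and SAP 3.1 still say 56 days.

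Four stronger readings are tempting, and the documents do not support them.

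- **That every exit up to Day 4 is forced into under-compliance.** Day 1 is exempt. The instruction to withhold the morning dose is tied to the next scheduled visit and is not repeated for the early termination visit in Protocol 8.4.11. If a morning dose is taken, Days 3 and 4 pass 80% and only Day 2 fails. Nothing indicates that such exits are common.
- **That no dose can precede Visit 6.** Protocol 8.4.7 provides for a subject who dosed anyway, by delaying procedures four hours. Such a completer can reach 113/114.
- **That compliance is understated for everyone.** Day 1 exits and never-dosed subjects have their own rules.
- **That the per-protocol population or recorded deviations are affected.** No document ties the SAP percentage to that population. Protocol 8.5 has the investigator record deviations from the ampoule count and does not refer to the SAP formula. The most that can be said is that site and SAP labels could differ near 80%.

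**Conclusion.** The point holds as a counting inconsistency of minor consequence. Compliance for a fully adherent Day 57 completer with no exit-day dose is understated by 1.8 percentage points and exposure overstated by one day. Misclassification at the 80% limit is confined, among Day 57 completers, to those with 90 or 91 doses; among fully adherent early exits, it affects Days 2 to 4 without an exit-day dose and Day 2 alone with one. For subjects who stop drug and stay in the study, the overstatement of exposure can be larger, but it cannot be sized from the documents. The primary analysis is unaffected.

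Two assumptions matter. First, the calculation uses true doses taken. SAP 12.1 derives them from vials dispensed, unused and missed, and its wording, read literally, has missed vials raising the count; a subject with 90 true doses need not then score 90/114. Second, the in-office Day 1 dose is taken to come from the dispensed kit. If it does not, perfect adherence with no exit-day dose scores lower still: 111/114 = 97.4% at Day 57 and 5/8 = 62.5% at Day 4.

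**What to change.** In SAP 12.1, for exits after Day 1, set expected doses to 2 × (exit date − Day 1), plus 1 if a dose is recorded on the exit day. Keep the existing Day 1 and never-dosed rules.

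In SAP 12.2, set exposure to date of last dose − Day 1 + 1. If no last-dose date is collected and no exit-day dose is recorded, use exit date − Day 1. That fallback removes the extra day but not any time off drug, so the last-dose date is preferable.

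The cost is a few lines in the SAP and the matching programming, plus possibly a last-dose date field on the eCRF. No efficacy analysis changes.

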13.1 Primary Analyses

The primary efficacy endpoints of this study include mean CFB to Day 57 of central corneal staining score (CCSS) and eye dryness score on Visual Analog Scale (EDS-VAS).

CCSS will be graded using the Ora Calibra® Corneal and Conjunctival Fluorescein Staining Scale. The Ora Calibra® Corneal and Conjunctival Staining Scale ranges from [REDACTED]

EDS will be subjectively graded by the subjects using the VAS at all scheduled visits. Subjects are asked to rate each ocular symptom due to ocular dryness by placing a vertical mark on the horizontal line to indicate the current level of discomfort. 0% corresponds to “no discomfort” and 100% corresponds to “maximal discomfort.”

For both endpoints, CFB to each post-baseline protocol visit ([Section 3.1](#)) will be calculated using actual scores and resulting scores from multiple imputation methodology specified in Estimand 1 ([Section 2.6](#)). The imputation methods will be performed using the SAS® procedure PROC MI. Refer to [Appendix 1](#) for examples of SAS® codes for obtaining randomized treatment group-based MCMC multiple imputation data.

CFB to a post-baseline visit timepoint will be calculated as Post-baseline visit result minus Baseline visit results

Note: Positive difference indicates a worsening of dry eye signs or symptoms. In addition, treatment comparisons between active and placebo will be calculated as Active minus Placebo, such that a negative result indicates a better score for the active treatment (i.e., tafanercept group demonstrated less severity in dry eye signs or symptoms than the placebo group).

13.1.1 CENTRAL CORNEAL STAINING SCORE (CCSS)

CCSS CFB to Day 57 will be analyzed using the ITT population with multiple imputation methodology specified in Estimand 1 ([Section 2.6](#)). The initial MMRM model will include terms for baseline CCSS, site, visit (as categorical term), treatment group and the interaction of treatment group and visit as fixed effects with correlated errors. The inclusion of site in the final model will be evaluated at an alpha level of 0.1. All post-baseline visits will be used in the model.

If site is retained in the final primary analyses, the site by treatment interaction will be explored in a separate analysis to evaluate how the treatment effect may differ across sites. All post-baseline visits will be used in the model.

An alternate MMRM will be executed as supportive analysis. This additional model will include all terms in the final model of the primary analyses with, [REDACTED]

Sensitivity analyses to compare CCSS CFB between treatment groups using imputation by Last Observation Carried Forward (LOCF), multiple imputation by placebo group-based pattern mixture models (PMM), and analyses of observed data only using the ITT and PP populations will be conducted.

The Least Square (LS) means, LS mean difference, Standard Errors (SEs), two-sided 95% CIs, and p-values of the LS mean difference will be reported from the MMRM model. Two-sample t-tests will also be conducted as supportive analyses of the mean CFB to Day 57. The sample means, sample mean difference, SEs, two-sided 95% CIs, and two-sided p-values will be reported from the two-sample t-test.

The MMRM LS means of the CCSS CFB in the study eye at Day 57 and CCSS CFB at each visit will be displayed graphically in a bar chart with SE bars by treatment group.

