If site is retained in the final primary analyses, the site by treatment interaction will be explored in a separate analysis to evaluate how the treatment effect may differ across sites. All post-baseline visits will be used in the model. Two-sample t-tests will also be conducted as supportive analyses.

Change from baseline of EDS from VAS at Day 57 ± 3 (V6, Week 8) between tanfanercept ophthalmic solution 0.25% and placebo will be analyzed as described for CFB of CCSS with adjustment for baseline EDS instead of baseline CCSS.

Example SAS code for the MMRM of the primary analyses is as follows:

```
PROC MIXED DATA = INDATA METHOD = REML;  
  CLASS SUBJID TREATMENT VISIT SITE;  
  MODEL CHG = BASELINE SITE VISIT|TREATMENT / DDFM = KR SOLUTION COVB;  
  REPEATED VISIT/SUBJECT = SUBJID TYPE = UN R RCORR;  
  LSMEANS TREATMENT TREATMENT*VISIT / CL PDIFF;  
RUN;
```

where

- *SUBJID* is the subject ID
- *TREATMENT* is the name of the treatment group variable
- *VISIT* is the visit
- *SITE* is the site id
- *CHG* is the change from baseline
- *BASELINE* is the baseline value

An alternate MMRM will be executed as a sensitivity analyses for both primary endpoints. These additional models will include all terms in the final models of the primary analyses.

Additional exploratory comparisons of the mean absolute scores of the primary endpoints at both Day 57 ± 3 (V6, Week 8) and baseline (V2) between the treatment groups will be conducted using two-sample t-tests and MMRM.

Least squares means and standard errors for each treatment group and for the difference between treatment groups will be presented from the MMRM together with two-sided p-values and 95% confidence intervals. Two-sided exact p-values and 95% confidence intervals will be presented from the permutation test with trimmed means.

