4.2 Masking and Unmasking

All subjects, investigators, and study personnel involved with the conduct of the study will be masked with regard to treatment assignments. When medically necessary, the investigator may need to determine what treatment arm has been assigned to a subject. When possible (i.e., in non-emergent situations), Ora and/or the study sponsor should be notified before unmasking study drug. The unmasked subject will be discontinued from the study.

5. Sample Size and Power Considerations

The primary objective of the study is to demonstrate a statistically significant difference between the active treatment and placebo.

Per the protocol, this study was expected to randomize 150 subjects in each of the two treatment arms, for a total of 300 randomized subjects. Assuming a 10% drop out rate, 135 subjects per group are expected to complete the study.

Assuming a common standard deviation (SD) in the change from baseline (Day 1) to Day 57 for CCSS of [REDACTED] a sample size of 135 evaluable subjects per group will have 99.4% power to detect a difference of [REDACTED] between the active treatment group and the placebo group at a significance level of 0.05.

After randomizing 260 subjects, the Sponsor conducted a masked interim assessment of the sample size ([section 3.1](#)). The power was recalculated based on the reduced sample size following the original assumptions described above.

After randomizing 130 subjects in each of the two treatment arms, for a total of 260 randomized subjects and assuming a 10% drop out rate, 119 subjects per group are expected to complete the study.

Assuming a common standard deviation (SD) in the change from baseline (Day 1) to Day 57 for CCSS of [REDACTED] a sample size of 119 evaluable subjects per group will have 98.7% power to detect a difference of [REDACTED] between the active treatment group and the placebo group at a significance level of 0.05.

6. Data Preparation

All the datasets used for the analyses and presentations of summary results will be implemented using Clinical Data Interchange Standards Consortium (CDISC, Implementation Guide [IG] Version 3.2) and the analysis data model (ADaM, Implementation Guide [IG] Version 2.0) format. The ADaM datasets will be created using SDTM datasets.

7. Analysis Populations

The following analysis populations will be considered:

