8.4 Data Analysis Conventions

All data analyses will be performed after the study is completed and the database has been locked and released for unmasking. Statistical programming and analyses will be performed using SAS® Version 9.4 or higher. Output will be provided in RTF (rich text format) for tables, listings, and figures using landscape orientation. All study data will be listed by subject, treatment, and visit (as applicable) based on all enrolled subjects unless otherwise specified.

All summaries will be presented by treatment group and visit where appropriate, unless otherwise specified. Listings will be presented for all data collected on the eCRFs, sorted by subject id number and visit.

Summaries for continuous and ordinal variables will include the number of observations (n), arithmetic mean, SD, median, minimum, and maximum. Minima and maxima will be reported with the same precision as the raw values; means and medians will be presented to one additional decimal place than reported in the raw values. Standard deviations will be presented to two additional decimal places than reported in the raw values. Summaries for discrete variables will include frequency counts and percentages. All percentages will be rounded to one decimal place (i.e., XX.X%).

All statistical tests will be two-sided with a significance level of 0.05 ($\alpha = 0.05$) unless otherwise specified. Confidence intervals (CI) will be two-sided at 95% confidence levels where appropriate. All p-values will be rounded to four decimal places; p-values less than 0.0001 will be presented as "<0.0001"; p-values greater than 0.9999 will be presented as ">0.9999."

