13.1.2 EYE DRYNESS SCORE ON VISUAL ANALOG SCALE (EDS-VAS)

EDS-VAS CFB to Day 57 will be analyzed as described above for the analysis of CCSS with adjustment for baseline EDS-VAS instead of CCSS. Estimand 2 will be used for the analysis of EDS-VAS in the presence of an imbalance of missing data between the two treatment groups ([Section 2.6](#)).

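### The primary MMRM text applies one baseline slope to all four post-baseline visits; if the baseline relation differs by visit, the Day 57 contrast loses a little precision that a baseline-by-visit term would recover

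*SAP*

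**What the plan says.** SAP 13.1.1 sets out the CCSS model: "The initial MMRM model will include terms for baseline CCSS, site, visit (as categorical term), treatment group and the interaction" of treatment and visit. It adds that every post-baseline visit enters the model, which means Visits 3 to 6. The example code in Protocol 10.4.5 has the same structure: "MODEL CHG = BASELINE SITE VISIT|TREATMENT". Treatment is crossed with visit and baseline is not. SAP 13.1.2 carries the form over to the symptom endpoint, "with adjustment for baseline EDS-VAS instead of CCSS". Protocol 10.4.5 starts from an unstructured covariance matrix.

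Two places are less clear. A supportive alternate MMRM is planned in SAP 13.1.1, but what it adds is redacted. SAP Appendix 1 gives code to be run on each imputed data set and calls it the MMRM. Its `CLASS` statement lists only `TREATMENT`, its `MODEL` line is redacted, and it defines the outcome as the Day 57 change.

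**The concern.** Only Day 57 supports the two primary claims, but the common slope is estimated from all four visits, three of which fall on or before Day 29. If change from baseline depends on baseline differently early and late in treatment, the fitted slope is a compromise that is wrong for Day 57. The part of the Day 57 variance that baseline could have explained then stays in the residual, and the standard error of the treatment difference grows.

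The plan allows this flexibility elsewhere. In Appendix 1 the imputation models use baseline jointly with Visits 3 to 6, and the placebo-based step regresses each visit separately on baseline and the earlier visits. Missing values would thus be imputed with visit-specific baseline relations and then analysed with one forced slope.

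What is at stake is precision on both primary contrasts. It could matter more for EDS, because the stated power covers CCSS only.

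**Working it through.** **Step 1: the plan's own power figures.** SAP Section 5 redacts the SD and the target difference, so only their ratio *d* can be recovered. The inputs are two-sided alpha 0.05 (SAP 8.4: "All statistical tests will be two-sided with a significance level of 0.05") and the first power statement: "a sample size of 135 evaluable subjects per group will have 99.4% power to detect a difference of" a redacted amount.

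- Normal approximation: d = (1.960 + 2.512) × √(2/135) = 0.544. The exact noncentral *t* gives 0.546.
- Predicted power at 119 per group: Φ(0.544 × √(119/2) − 1.960) = 98.7%.

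This agrees with the second statement, "a sample size of 119 evaluable subjects per group will have 98.7% power to detect a difference of" a redacted amount. The two figures are mutually consistent, although neither can be rebuilt from its own redacted inputs.

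**Step 2: size of the loss.** The documents give no baseline slope or correlation by visit, so these values are assumed. Baseline and outcome are given unit SD at every visit. Let r₄ be the baseline correlation at Day 57 and g the common slope, on the raw-score scale, to which the unstructured-covariance model converges. Then

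residual variance at Day 57, visit-specific slope = 1 − r₄²

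residual variance at Day 57, common slope = (1 − r₄²) + (r₄ − g)²

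SE ratio = √[1 + (r₄ − g)² / (1 − r₄²)]

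Worked case, correlations 0.70, 0.65, 0.55, 0.40 with residual correlation 0.5: g = 0.635. The ratio is √[1 + 0.235²/0.84] = √1.0657 = 1.032. On the change scale the true Day 57 slope is 0.40 − 1 = −0.60 and the fitted slope is 0.635 − 1 = −0.365, so change is under-adjusted.

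The ranges below cover three residual correlation patterns: compound symmetry 0.5, compound symmetry 0.2, and autoregressive 0.8. The power column treats 99.4% as the power of the model with visit-specific slopes and divides *d* by the SE ratio, at 135 per group.

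| Correlation, Week 1 to Week 8 | SE ratio at Day 57 | CCSS power with common slope |
|---|---|---|
| 0.5, flat | 1.000 | 99.4% |
| 0.55 to 0.45 | 1.002 | 99.4% |
| 0.6 to 0.4 | 1.009-1.011 | 99.3% |
| 0.7 to 0.4 | 1.025-1.032 | 99.1-99.2% |
| 0.7 to 0.3 | 1.039-1.053 | 98.9-99.0% |
| 0.8 to 0.2 (extreme) | 1.10-1.15 | 97.4-98.3% |

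**Step 3: simulation check.** This used 270 subjects, complete data, 1,000 runs per scenario and residual correlation 0.5. The scenarios were flat 0.5, 0.6-0.4, 0.7-0.4, 0.7-0.3 and 0.8-0.2.

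- Ratios of mean model SE: 1.000, 1.011, 1.032, 1.052 and 1.141.
- Ratios of empirical SE: 0.997, 1.006, 1.031, 1.032 and 1.147. The 0.7-0.3 case is lower here than by the model SE.
- Rejection rate under the null: 4.2-5.6% with the common slope and 4.2-5.7% with visit-specific slopes. The Monte Carlo error is √(0.05 × 0.95/1000) = 0.7 points, so neither model shows a type I error problem.

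**Step 4: EDS.** No power is stated. Purely as an illustration, suppose EDS power were 80% with the interaction, so that the standardised effect is 1.960 + 0.842 = 2.802.

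- SE ratio 1.011: Φ(2.802/1.011 − 1.960) = 79.1%.
- SE ratio 1.053: Φ(2.802/1.053 − 1.960) = 75.8%.

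**The case against.** The strongest reply is that a main-effect baseline term is a valid pre-specified choice and nothing in the documents shows that it costs anything. That largely stands. A reader might infer that the baseline relation must weaken over eight weeks and that the error bars are therefore wider than necessary in this trial. The documents give no baseline relation by visit, so that inference has no support here, and with equal slopes the loss is zero. A reader might also infer bias or an invalid test. Neither follows: randomization protects the comparison, and the unstructured covariance gives Day 57 its own variance, which absorbs the misfit.

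For CCSS the loss is probably at the low end. Eligibility limits on CCSS (Protocol 5.3) probably narrow its spread, and for given slopes the misfit term shrinks in proportion to baseline variance. Randomization is also stratified on Visit 2 study-eye CCSS (Protocol 8.4.3), which limits chance imbalance between arms. Neither argument carries over directly to EDS, since no listed entry criterion or stratum uses the EDS scale.

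The redacted alternate MMRM might contain the interaction, so one cannot say that the term is absent from the whole plan. That model is only supportive, however, and the point concerns the primary one.

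Finally, the Appendix 1 code looks like a single-visit model. If that is what will be run, Day 57 has its own slope and the issue disappears. But its `MODEL` line is redacted, and the SAP body requires all post-baseline visits. The two need reconciling, and the repeated-measures text cannot be set aside on the strength of that code.

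**Conclusion.** The point holds as a conditional, optional improvement in efficiency. As written, the primary MMRM for both endpoints has one baseline slope for four visits. If the true slopes differ, the Day 57 standard error is larger by about 1% for a mild fall in correlation and by about 2.5-5% for a marked one. Only an extreme fall, from 0.8 to 0.2, gives 10-15%. For CCSS that is about half a point or less of the stated 99.4% power outside the extreme case, where it is at most about two points. For EDS the documents give no basis for sizing the loss.

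These figures rest on assumed correlations, equal baseline and outcome SDs, and complete data. They are not estimates for this trial.

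**What to change.** Before unmasking, specify the primary MMRM for CCSS and EDS with fixed effects `BASELINE VISIT BASELINE*VISIT TREATMENT TREATMENT*VISIT`, plus site if it is retained. Four slopes replace one, so the cost is three parameters. No new data are needed, and practically nothing is lost if the slopes turn out equal.

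In the same revision, make the Appendix 1 code for the imputed data sets match that model: subject and visit in `CLASS`, change at every post-baseline visit as the outcome, a `REPEATED` statement, and the treatment difference taken at Day 57. Align the observed-data example too, since its baseline term is likewise not crossed with week. Record the added term in SAP Section 18 as a change from the protocol-stated analysis.
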